Appendix 14: Study Details Specific to RO7247669 2100 mg+Tira Arm (Cohorts 1 and 2)

A14–4.2 CONCOMITANT THERAPY FOR RO7247669 2100 mg+TIRA ARM

Concomitant therapy consists of any medication (e.g., prescription drugs, over-the-counter drugs, vaccines, herbal or homeopathic remedies, nutritional supplements) used by a patient in addition to protocol-mandated study treatment from 7 days prior to initiation of study treatment to the treatment discontinuation visit. All such medications should be reported to the investigator and recorded on the Concomitant Medications eCRF.

A14–4.2.1 Permitted Therapy for RO7247669 2100 mg+Tira Arm

Patients are permitted to use the following therapies during the study:

- Oral contraceptives with a failure rate of <1% per year
- Hormone-replacement therapy
- Prophylactic or therapeutic anticoagulation therapy (such as warfarin at a stable dose or low-molecular-weight heparin)
- Vaccinations (such as influenza, COVID-19)
 - Live, attenuated vaccines are not permitted (see Section [A14–4.2.4](#))
- Megestrol acetate administered as an appetite stimulant
- Mineralocorticoids (e.g., fludrocortisone)
- Corticosteroids administered for chronic obstructive pulmonary disease (COPD) or asthma
- Low-dose corticosteroids administered for orthostatic hypotension or adrenocortical insufficiency. Other use of corticosteroids may be permitted at the investigator's discretion. The Medical Monitor is available to advise as needed
- Local therapy (e.g., surgery other than complete lymph node dissection [CLND] that is not considered to be related to melanoma)

A14–4.2.2 Additional Permitted Therapy for RO7247669 2100 mg+Tira Arm in Cohort 2

Patients are permitted to use the following therapies during the study:

- Palliative radiotherapy (e.g., treatment of known bony metastases or symptomatic relief of pain) as outlined below:

Palliative radiotherapy is permitted, provided it does not interfere with the assessment of tumor target lesions (e.g., the lesion to be irradiated must not be the only site of measurable disease). Treatment with tiragolumab may be continued during palliative radiotherapy.

Appendix 14: Study Details Specific to RO7247669 2100 mg + Tira Arm (Cohorts 1 and 2)

Treatment with RO7247669 may be continued during palliative radiotherapy with one exception: palliative radiotherapy is not permitted on days when RO7247669 is administered.

- Local therapy (e.g., surgery, stereotactic radiosurgery, radiotherapy, radiofrequency ablation) as outlined below:

Patients experiencing a mixed response requiring local therapy for control of three or fewer lesions may still be eligible to continue study treatment. Patients who receive local therapy directed at a target lesion will no longer be evaluable for radiographic response but will remain evaluable for progression.

Premedication with antihistamines, antipyretics, and/or analgesics may be administered for the second and subsequent RO7247669 and tiragolumab infusions only, at the discretion of the investigator.

In general, investigators should manage a patient's care (including preexisting conditions) with supportive therapies other than those defined as cautionary or prohibited therapies as clinically indicated, per local standard practice. Patients who experience infusion-associated symptoms may be treated symptomatically with acetaminophen, ibuprofen, diphenhydramine, and/or H₂-receptor antagonists (e.g., famotidine, cimetidine), or equivalent medications per local standard practice. Serious infusion-associated events manifested by dyspnea, hypotension, wheezing, bronchospasm, tachycardia, reduced oxygen saturation, or respiratory distress should be managed with supportive therapies as clinically indicated (e.g., supplemental oxygen and β2-adrenergic agonists; refer to [Appendix 8](#) for details).

A14–4.2.3 Cautionary Therapy for RO7247669 2100 mg + Tira Arm

A14–4.2.3.1 Corticosteroids, Immunosuppressive Medications, and Tumor Necrosis Factor-α Inhibitors

Systemic corticosteroids, immunosuppressive medications, and tumor necrosis factor-α (TNF-α) inhibitors may attenuate potential beneficial immunologic effects of treatment with RO7247669 and/or tiragolumab. Therefore, in situations in which systemic corticosteroids, immunosuppressive medications, or TNF-α inhibitors would be routinely administered, alternatives, including antihistamines, should be considered. If the alternatives are not feasible, systemic corticosteroids, immunosuppressive medications, and TNF-α inhibitors may be administered at the discretion of the investigator.

Systemic corticosteroids or immunosuppressive medications, are recommended, at the discretion of the investigator, for the treatment of specific adverse events when associated with RO7247669 and/or tiragolumab therapy (refer to [Appendix 9](#) for details).

Appendix 14: Study Details Specific to RO7247669 2100 mg + Tira Arm (Cohorts 1 and 2)

A14–4.2.3.2 Herbal Therapies

Concomitant use of herbal therapies is not recommended because their pharmacokinetics, safety profiles, and potential drug-drug interactions are generally unknown. However, herbal therapies not intended for the treatment of cancer (see Section A14–4.2.3) may be used during the study at the discretion of the investigator.

A14–4.2.4 Prohibited Therapy for RO7247669 2100 mg + Tira Arm

Use of the following concomitant therapies is prohibited as described below:

- Concomitant therapy intended for the treatment of cancer (including, but not limited to, chemotherapy, hormonal therapy, immunotherapy, radiotherapy, and herbal therapy), whether health authority–approved or experimental, is prohibited for various time periods prior to starting study treatment, depending on the agent (see Section 4.4), and during study treatment until surgery, or unacceptable toxicity (Cohort 1), or until disease progression is documented and the patient has discontinued study treatment (Cohort 2), with the exception of palliative radiotherapy (see Section A14–4.2.1 for details).
- Investigational therapy is prohibited within 28 days prior to initiation of study treatment and during study treatment.
- Live, attenuated vaccines (e.g., FluMist®) are prohibited within 4 weeks prior to initiation of study treatment, during treatment with RO7247669 and/or tiragolumab, and for 4 months after the last dose of RO7247669 and/or tiragolumab.
- Systemic immunostimulatory agents (including, but not limited to, interferons and interleukin-2) are prohibited within 4 weeks or 5 half-lives of the drug (whichever is longer) prior to initiation of study treatment and during study treatment because these agents could potentially increase the risk for autoimmune conditions when given in combination with RO7247669 and/or tiragolumab.

A14–4.3 **CONTRACEPTION REQUIREMENTS FOR RO7247669 2100 mg + TIRA ARM**

Contraception requirements for women and men in the RO7247669 2100 mg + Tira arm are outlined below:

- For women of childbearing potential: agreement to remain abstinent (refrain from heterosexual intercourse) or use contraception, as defined below:

Women must remain abstinent or use contraceptive methods with a failure rate of < 1% per year during the treatment period, for 4 months after the last dose of RO7247669, and for 90 days after the last dose of tiragolumab.

A woman is considered to be of childbearing potential if she is postmenarcheal, has not reached a postmenopausal state (≥ 12 continuous months of amenorrhea with no identified cause other than menopause), and is not permanently infertile due to surgery (i.e., removal of ovaries, fallopian tubes,

Appendix 14: Study Details Specific to RO7247669 2100 mg+Tira Arm (Cohorts 1 and 2)

and/or uterus) or another cause as determined by the investigator (e.g., Müllerian agenesis). The definition of childbearing potential may be adapted for alignment with local guidelines or regulations.

Examples of contraceptive methods with a failure rate of <1% per year include bilateral tubal ligation, male sterilization, hormonal contraceptives that inhibit ovulation, hormone-releasing intrauterine devices, and copper intrauterine devices.

The reliability of sexual abstinence should be evaluated in relation to the duration of the clinical trial and the preferred and usual lifestyle of the patient. Periodic abstinence (e.g., calendar, ovulation, symptothermal, or postovulation methods) and withdrawal are not acceptable methods of contraception.

If required per local guidelines or regulations, locally recognized acceptable methods of contraception and information about the reliability of abstinence will be described in the local Informed Consent Form.

- For men: agreement to remain abstinent (refrain from heterosexual intercourse) or use contraception, and agreement to refrain from donating sperm, as defined below:

With a female partner of childbearing potential who is not pregnant or a pregnant female partner, men who are not surgically sterile must remain abstinent or use a condom plus an additional contraceptive method that together result in a failure rate of <1% per year during the treatment period, for 4 months after the last dose of RO7247669, and for 90 days after the last dose of tiragolumab to avoid exposing the embryo. Men must refrain from donating sperm during this same period.

The reliability of sexual abstinence should be evaluated in relation to the duration of the clinical trial and the preferred and usual lifestyle of the patient. Periodic abstinence (e.g., calendar, ovulation, symptothermal, or postovulation methods) and withdrawal are not acceptable methods of preventing drug exposure. If required per local guidelines or regulations, information about the reliability of abstinence will be described in the local Informed Consent Form.

A14-5 ASSESSMENT OF SAFETY FOR RO7247669 2100 mg+TIRA ARM

A14-5.1 SAFETY PLAN FOR RO7247669 2100 mg+TIRA ARM

The safety plan for patients in this study is based on clinical experience with RO7247669 and tiragolumab in completed and ongoing studies. The anticipated important safety risks are outlined below (see Sections A14-5.1.1, A14-5.1.2, A14-5.1.3, and A14-5.1.4). Guidelines for the management of patients who experience specific adverse events are provided in Section A14-5.1.4 and Appendix 9.

Measures will be taken to ensure the safety of patients participating in this study, including the use of stringent inclusion and exclusion criteria and close monitoring of

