Appendix 12: Study Details Specific to RO7247669 2100 mg Arm

A12–4.3 CONTRACEPTION REQUIREMENTS FOR RO7247669 2100 mg ARM

Contraception requirements for women and men in the RO7247669 2100 mg arm are outlined below:

- For women of childbearing potential: agreement to remain abstinent (refrain from heterosexual intercourse) or use contraception, as defined below:

Women must remain abstinent or use contraceptive methods with a failure rate of < 1% per year during the treatment period and for 4 months after the final dose of RO7247669.

A woman is considered to be of childbearing potential if she is postmenarcheal, has not reached a postmenopausal state (≥ 12 continuous months of amenorrhea with no identified cause other than menopause), and is not permanently infertile due to surgery (i.e., removal of ovaries, fallopian tubes, and/or uterus) or another cause as determined by the investigator (e.g., Müllerian agenesis). The definition of childbearing potential may be adapted for alignment with local guidelines or regulations.

Examples of contraceptive methods with a failure rate of < 1% per year include bilateral tubal ligation, male sterilization, hormonal contraceptives that inhibit ovulation, hormone-releasing intrauterine devices, and copper intrauterine devices.

The reliability of sexual abstinence should be evaluated in relation to the duration of the clinical trial and the preferred and usual lifestyle of the patient. Periodic abstinence (e.g., calendar, ovulation, symptothermal, or postovulation methods) and withdrawal are not acceptable methods of contraception.

If required per local guidelines or regulations, locally recognized acceptable methods of contraception and information about the reliability of abstinence will be described in the local Informed Consent Form.

- For men: agreement to remain abstinent (refrain from heterosexual intercourse) or use contraception, and agreement to refrain from donating sperm, as defined below:

With a female partner of childbearing potential who is not pregnant or a pregnant female partner, men who are not surgically sterile must remain abstinent or use a condom plus an additional contraceptive method that together result in a failure rate of < 1% per year during the treatment period, for 4 months after the last dose of RO7247669 to avoid exposing the embryo. Men must refrain from donating sperm during this same period.

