Appendix 13: Study Details Specific to Atezo + Tira Arm

A13–4.3 CONTRACEPTION REQUIREMENTS FOR ATEZO + TIRA ARM

Contraception requirements for men and women in the Atezo + Tira arm are outlined below:

- For women of childbearing potential: agreement to remain abstinent (refrain from heterosexual intercourse) or use contraception, as defined below:

Women must remain abstinent or use contraceptive methods with a failure rate of < 1% per year during the treatment period and for 5 months after the final dose of atezolizumab and for 90 days after the final dose of tiragolumab.

A woman is considered to be of childbearing potential if she is postmenarcheal, has not reached a postmenopausal state (≥ 12 continuous months of amenorrhea with no identified cause other than menopause), and is not permanently infertile due to surgery (i.e., removal of ovaries, fallopian tubes, and/or uterus) or another cause as determined by the investigator (e.g., Müllerian agenesis). The definition of childbearing potential may be adapted for alignment with local guidelines or regulations.

Examples of contraceptive methods with a failure rate of < 1% per year include bilateral tubal ligation, male sterilization, hormonal contraceptives that inhibit ovulation, hormone-releasing intrauterine devices, and copper intrauterine devices.

The reliability of sexual abstinence should be evaluated in relation to the duration of the clinical trial and the preferred and usual lifestyle of the patient. Periodic abstinence (e.g., calendar, ovulation, symptothermal, or postovulation methods) and withdrawal are not acceptable methods of contraception.

If required per local guidelines or regulations, locally recognized acceptable methods of contraception and information about the reliability of abstinence will be described in the local Informed Consent Form.

- For men: agreement to remain abstinent (refrain from heterosexual intercourse) or use a condom, and agreement to refrain from donating sperm, as defined below:

With a female partner of childbearing potential or pregnant female partner, men must remain abstinent or use a condom during the treatment period and for 90 days after the final dose of tiragolumab. Men must refrain from donating sperm during this same period.

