Appendix 14: Study Details Specific to RO7247669 2100 mg + Tira Arm (Cohorts 1 and 2)

patients during the study. Because of the potential for overlapping toxicities for RO7247669 and tiragolumab, special caution will be taken by performing a planned safety run-in for patients randomized to this arm in Cohort 2, and a planned safety evaluation phase in Cohort 1 (see Section 3.1.4).

Administration of RO7247669 and tiragolumab will be performed in a monitored setting in which there is immediate access to trained personnel and adequate equipment and medicine to manage potentially serious reactions. Adverse events will be reported as described in Sections 5.2–5.6.

A14–5.1.1 Risks Associated with RO7247669

Clinical evaluation of RO7247669 is ongoing, and not all risks are known. As an antagonist of PD-1 and LAG-3, RO7247669 is anticipated to enhance T-cell and NK-cell proliferation, survival, and function. Based on the mechanism-of-action of RO7247669, the safety profile is anticipated to be similar to other CPIs. Potential risks associated with RO7247669 include the following: IRRs (including anaphylaxis), immunogenicity, and immune-mediated adverse events. Refer to Section 6 of the RO7247669 Investigator's Brochure for a detailed description of anticipated safety risks for RO7247669.

A14–5.1.1.1 Infusion-Related Reactions and Anaphylaxis

Administration of therapeutic antibodies may cause IRRs, which may include symptoms such as fever, chills, hypotension, shortness of breath, skin rash, headache, nausea, and vomiting. Such reactions typically occur during or shortly after the infusion and are predominantly reported following the first infusion. The incidence and severity of IRRs typically decrease with subsequent infusions. Based on in vitro data, the risk of proinflammatory cytokine-mediated IRRs on first administration of RO7247669 as single agent is considered low.

Refer to Section A14–4.1.2 for detailed guidance on administration of RO7247669 in this study. Refer to Appendix 8 for guidance on anaphylaxis precautions and Section A14–5.1.4.3 for guidance on the management of IRRs.

A14–5.1.1.2 Immunogenicity

Administration of therapeutic antibodies may cause the formation of anti-drug antibodies, which may negatively affect the safety of the therapeutic (e.g., allergic reactions, immune complex-mediated diseases).

A14–5.1.1.3 Immune-Mediated Adverse Events

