Appendix 14: Study Details Specific to RO7247669 2100 mg + Tira Arm (Cohorts 1 and 2)

Suggested management guidelines for individual suspected immune-mediated adverse events are provided in [Appendix 9](#).

A14–5.1.2.4 Lymphopenia

The IgG1 backbone of tiragolumab with intact Fc-effector function may lead to ADCC-mediated reduction in lymphocyte count. Lymphopenia is a potential risk with tiragolumab. Transient decreases in lymphocyte count without clinical sequelae have been observed in patients treated with tiragolumab.

Patients with a lymphocyte count $<0.5 \times 10^9/L$ (500/ μ L) will be excluded from the study (see Section 4.1.1), and complete blood counts will be monitored regularly during the study (see Appendix A14–6).

A14–5.1.2.5 Embryofetal Toxicity

Embryofetal toxicity is a potential risk with tiragolumab. Administration of tiragolumab is expected to have adverse effects on pregnancy based on the expression of TIGIT on decidual NK and CD8+ T cells (Powell et al. 2017; van der Zwan et al. 2018; Vento-Tormo et al. 2018), and the expected role of these cells in the recognition and response to foreign fetal, placental, and viral antigens at the maternal-fetal interface as well as maintenance of maternal-fetal tolerance. No reproductive or teratogenicity studies in animals have been conducted with tiragolumab. There are no clinical studies of tiragolumab in pregnant women. Tiragolumab should not be administered to pregnant women.

Refer to Section 6 of the Tiragolumab Investigator's Brochure for a detailed description of embryofetal toxicity.

A14–5.1.3 Risks Associated with Combination Use of RO7247669 and Tiragolumab

The blockade of inhibitory checkpoints leads to increase adaptive T-cell immune responses via complementary targets, and the combination targeting multiple checkpoints may be associated with heightened immune-mediated toxicity relative to either agent alone. Such toxicity could manifest as a higher incidence or greater severity of autoimmune inflammation events, or potentially the development of HLH and MAS. The following adverse events are potential overlapping toxicities associated with combination use of RO7247669 plus tiragolumab: IRR and immune-mediated toxicities, (see [Appendix 9](#) for complete list).

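### The exemption for surgically sterile men in A14-4.3 and A16-4.3 (and, more weakly, A12-4.3 and A15-4.3) also covers men with a pregnant partner, where it does not serve the rule's stated aim

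*Combined protocol and SAP*

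**What the plan says.** A14-4.3 (RO7247669 2100 mg + Tira) sets the men's duty in a single sentence. It begins "With a female partner of childbearing potential who is not pregnant or a pregnant female partner, men who are not surgically sterile must remain abstinent", and the alternative to abstinence is to "use a condom plus an additional contraceptive method that together result in a failure rate" below 1% per year. The duty runs through treatment and then "for 4 months after the last dose of RO7247669, and for 90 days after the last dose of tiragolumab to avoid exposing the embryo". The next paragraph says that periodic abstinence and "withdrawal are not acceptable methods of preventing drug exposure". A16-4.3 (RO7247669 600 mg + Tira) has the same text.

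A12-4.3 and A15-4.3 (RO7247669 alone, 2100 mg and 600 mg) use the same construction and the same exemption, with one follow-on period: "for 4 months after the last dose of RO7247669 to avoid exposing the embryo".

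A13-4.3 (Atezo + Tira) is worded differently: "With a female partner of childbearing potential or pregnant female partner, men must remain abstinent or use a condom during the treatment period". The duty there ends 90 days after the final tiragolumab dose. It has no exemption for sterile men.

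On risk, A14-5.1.2.5 states "Embryofetal toxicity is a potential risk with tiragolumab", and A13 and A16 carry the same account. For RO7247669, A14-5.1.1 states "Potential risks associated with RO7247669 include the following: IRRs (including anaphylaxis), immunogenicity, and immune-mediated adverse events". A12, A15 and A16 give the same list. Embryofetal toxicity is not on it, although those sections also say that not all risks are known.

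**The concern.** The sentence joins two situations that need different protection. With a partner who could conceive, a man's sterility answers the contraceptive question. With a partner who is already pregnant, there is no conception left to prevent, and the only remaining purpose is to keep drug away from the embryo. The exemption applies to both.

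A site that follows A14-4.3 or A16-4.3 literally places no abstinence or condom duty on a surgically sterile man whose partner is pregnant. In the Atezo + Tira arm the same man, on the same tiragolumab dose, would have that duty. At stake is a precaution for a third party. A14-5.3.4 and A16-5.3.4 make a birth defect in a partner's child a reportable serious adverse event, but that detects harm and does not prevent it.

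**Working it through.** No formula applies, and the plan states no figure to reproduce. The check sets the five arm-specific rules side by side.

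| Section | Treatment (every 3 weeks) | Men bound if the partner is pregnant | Duty | Period after last dose | Embryofetal toxicity named for a drug in the arm |
|---|---|---|---|---|---|
| A12-4.3 | RO7247669 2100 mg | non-sterile only | abstinence, or condom plus second method | 4 months | no |
| A13-4.3 | atezolizumab 1200 mg + tiragolumab 600 mg | all | abstinence or condom | 90 days (tiragolumab) | yes |
| A14-4.3 | RO7247669 2100 mg + tiragolumab 600 mg | non-sterile only | abstinence, or condom plus second method | 4 months (RO7247669), 90 days (tiragolumab) | yes |
| A15-4.3 | RO7247669 600 mg | non-sterile only | abstinence, or condom plus second method | 4 months | no |
| A16-4.3 | RO7247669 600 mg + tiragolumab 600 mg | non-sterile only | abstinence, or condom plus second method | 4 months (RO7247669), 90 days (tiragolumab) | yes |

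1. **Who is left out.** Four of the five sections (A12, A14, A15, A16) name a pregnant partner and then bind only men who are not sterile. The exempt group with a pregnant partner therefore has no abstinence or condom duty.

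2. **What the rule is for.** The sentence gives its own aim, which concerns exposure of the embryo. The paragraph after it describes the men's measures as preventing drug exposure, while the parallel paragraph for women speaks of contraception. A13-4.3 uses the same exposure phrase for men, so the phrase shows the purpose of the rule and not a difference between arms.

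3. **What sterility does.** Each appendix lists male sterilization among contraceptive methods with a failure rate below 1% per year. Nothing in the text available says that sterility limits exposure of a partner.

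4. **Same drug, different rule.** A13, A14 and A16 give tiragolumab at the same dose and interval, use the same 90-day period and describe the embryofetal risk identically. A13 binds all men, whereas A14 and A16 exempt sterile men. None of the three gives a reason.

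5. **Which period matters.** In A14 and A16 both drugs are given on Day 1 and are to be withheld or stopped together. Four calendar months are at least 120 days (for example February to May, 28 + 31 + 30 + 31 = 120), which exceeds 90, so the RO7247669 period governs. The tiragolumab period adds no further time. Its relevance is that it belongs to the drug with the named risk.

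6. **RO7247669 alone.** In A12 and A15, steps 1 to 3 hold, but there is no named embryofetal risk and no step 4 comparison. These two sections rest on the stated aim only.

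**The case against.** The strongest objection is that the concern matters clinically only if drug in a sterile man's semen can reach a pregnant partner in a relevant amount. The documents give no transfer data, and the embryofetal text concerns giving tiragolumab to pregnant women. This stands: a reader might infer that the plan exposes embryos to a demonstrated hazard, and the documents do not show that. What survives is narrower. The sponsor already imposes the duty on non-sterile men with pregnant partners, and sterility does not explain why other men should be free of it.

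Second, Section 4.1 and the consent form are not in the text available and may hold a general rule for men. This also stands. If they do, the gap becomes an inconsistency between documents.

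Third, A13 is an imperfect comparator. For non-sterile men A14 and A16 are stricter, since they require a second method. A13 also has no sterility exemption when the partner is not pregnant. A reader might conclude that A14 and A16 are laxer overall, or that the exemption should go altogether. Neither follows: with a partner who is not pregnant, the exemption fits a contraceptive purpose.

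Fourth, the RO7247669 rule may come from a different drug-specific template. That is plausible, but no text says so, and the sentence in A14 and A16 also governs the tiragolumab period.

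None of the four appendices exempts sterile men from the ban on sperm donation, so that safeguard is unaffected.

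**Conclusion.** The point holds as a low-severity defect of wording. In A14-4.3 and A16-4.3 a stated rule misses its own aim for one group of men, and it departs without explanation, in the text available, from the rule for the same tiragolumab regimen in A13-4.3. In A12-4.3 and A15-4.3 the same sentence misses its aim, but the support is weaker; a reader might treat all four sections as equally affected, and the evidence does not allow that.

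The size of the risk is unknown. The number of men who are both surgically sterile and have a pregnant partner is not given and is expected to be small. Counting the days for which such a man has no duty would only restate the length of the existing duty period and would measure neither exposure nor risk. Endpoints and analyses are not affected.

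The conclusion assumes that Section 4.1 and the consent form do not already impose the duty, and that the sponsor intends the stated aim to apply to pregnant partners, as naming them implies.

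**What to change.** Leave the current sentence unchanged and add one to A14-4.3 and A16-4.3, and for consistency to A12-4.3 and A15-4.3, to this effect: *a surgically sterile man whose partner is pregnant is to abstain or wear a condom while on treatment and until 4 months after his last RO7247669 dose*. In A14 and A16, add the period of 90 days after the last tiragolumab dose. Keep the sperm-donation ban as it is, and align Section 4.1 and the consent form.

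This only adds protection. Rewriting the sentence so that all men with a pregnant partner follow a condom-only rule would drop the second method now required of non-sterile men, which the gap does not call for.

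The cost is one sentence in each of four appendices and matching consent text, with no new visits or procedures. The downside is a condom or abstinence duty for a few more men.
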